5.3.5.2 Clinical Protocol

8. ASSESSMENT OF SAFETY

8.1. Safety Parameters

Safety will be characterized in terms of the incidence, timing, severity (graded by the National Cancer Institute [NCI] Common Terminology Criteria for Adverse Events [CTCAE], Version 4.0), seriousness, and relatedness of adverse events and laboratory abnormalities. In addition, physical examination, vital signs, and ECOG performance status will be serially monitored. Laboratory safety analyses will be based on the local laboratory data, and will include hematology, serum chemistry (including liver and kidney function), urinalysis, serum or urine pregnancy testing, and coagulation profile. Serum will also be assessed for immunogenicity to TRC105 (including anti-product antibody titers). In addition, single tracing 12-lead ECGs will be performed at the time-points indicated in the Schedule of Assessments ([Table 4](#), [Table 5](#), [Table 6](#) and [Table 7](#)). QT, PR and QRS intervals and heart rate will be captured. ECGs will also be collected as clinically indicated throughout the study.

8.1.1. Laboratory Safety Assessments

Abnormal and clinically significant laboratory tests should be recorded as adverse events. To meet the definition of clinically significant, the test result generally requires a change in medical management (e.g. new medication, unplanned treatment, additional tests, etc.).

8.1.1.1. Hematology, Serum Chemistry, Coagulation, Pregnancy Test

Assessments will be performed at the time points indicated in the Schedule of Assessments ([Table 4](#), [Table 5](#), [Table 6](#) and [Table 7](#)) and analyzed at local laboratories. Investigators may have additional blood tests performed for the purpose of planning treatment administration, or for following adverse events as clinically indicated.

- Hematology: CBC with differential and platelet count. Iron studies (serum iron, ferritin and total iron binding capacity).
- Coagulation: International Normalized Ratio (INR) will be assessed
- Serum Chemistry: Total bilirubin, alanine transaminase (ALT), aspartate transaminase (AST), alkaline phosphatase, lipase, amylase, total protein, albumin, sodium, potassium, bicarbonate, chloride, calcium, phosphorus, blood urea nitrogen, creatinine, magnesium, thyroid stimulating hormone and glucose
- Pregnancy Test: Serum or urine pregnancy tests will be performed locally on all female patients of childbearing potential. Patients must be surgically sterile (i.e.: hysterectomy) or be postmenopausal, or must agree to use effective contraception during the study and for 3 months following last dose of TRC105. The definition of effective contraception will be based on the judgment of the Principal Investigator or a designated associate.

8.1.1.2. Urinalysis

Urinalysis (without microscopic analysis, unless indicated) will be performed at time points indicated in the Schedule of Assessments ([Table 4](#), [Table 5](#), [Table 6](#) and [Table 7](#)) and analyzed

5.3.5.2 Clinical Protocol

by local laboratories. Microscopic analysis, urine protein-creatinine ratio (UPCR), and 24 urine collection for protein should be performed as clinically indicated.

8.1.1.3. Physical Examination

A physical examination including, but not limited to, general appearance, head, eyes, ears, nose, throat, neck, heart, chest, abdomen, musculoskeletal, extremities, skin, lymph nodes, neurological genitourinary (as appropriate), and rectal (as appropriate) will be assessed at timepoints indicated within the Schedule of Assessments (Table 4, Table 5, Table 6 and Table 7). The physical examination will include examination of known and suspected sites of disease.

8.1.1.4. Vital Signs

Heart rate, temperature, blood pressure, respiratory rate and weight will be assessed at time points indicated within the Schedule of Assessments (Table 4, Table 5, Table 6 and Table 7). Heart rate, temperature, blood pressure, and respiratory rate will also be assessed during TRC105 infusions as described in Section 4.1.2.2 and the footnotes of Table 4, Table 5, Table 6 and Table 7(Schedule of Assessments).

8.1.1.5. Performance Status

The ECOG scale will be used to assess performance status at Screening.

8.1.1.6. ECG

A single 12-lead (with a 10-second rhythm strip) tracing will be used for all ECGs. It is preferable that the machine used has a capacity to calculate standard intervals automatically. ECG will be performed at the time-points indicated in the Schedule of Assessments (Table 4, Table 5, Table 6 and Table 7) and as clinically indicated throughout the study.

8.2. Adverse Events

All observed or volunteered adverse events regardless of suspected causal relationship to TRC105 study drug will be reported as described below.

8.2.1. Definition of Adverse Event

An adverse event is any untoward medical occurrence in a trial patient who is administered a drug or biologic (medicinal product); the event may or may not have a causal relationship with the medicinal product. Examples of adverse events include, but are not limited to the following:

- Clinically significant symptoms and signs including:
 - Worsening of signs and symptoms of the malignancy under trial (disease progression without worsening of signs and symptoms assessed by measurement of malignant lesions on radiographs or other methods should not be reported as adverse events).
 - Signs and symptoms resulting from drug overdose, abuse, misuse, withdrawal, sensitivity, dependency, interaction or toxicity.

5.3.5.2 Clinical Protocol

- All possibly related and unrelated illnesses, including the worsening of a preexisting illness.
- Injury or accidents. Note that if a medical condition is known to have caused the injury or accident (hip fracture from a fall secondary to dizziness), the medical condition (dizziness) and the outcome of the accident (hip fracture from a fall) should be reported as 2 separate adverse events.
- Symptoms or signs resulting from exposure *in utero*.
- Abnormalities in physiological testing or physical examination findings that require clinical intervention or further investigation (beyond ordering a repeat confirmatory test).
- Laboratory abnormalities that meet any of the following (Note: merely repeating an abnormal test, in the absence of any of the below conditions, does not constitute an adverse event. Any abnormal test result that is determined to be an error does not require reporting as an adverse event.):
 - Test result that is associated with accompanying symptoms
 - Test result that requires additional diagnostic testing or medical/surgical intervention
 - Test result that leads to a change in TRC105 study drug dosing outside of protocol-stipulated dose adjustments or discontinuation from the trial, significant additional concomitant drug treatment, or other therapy
 - Test result that is considered to be an adverse event by the Investigator or TRACON

8.2.2. Serious Adverse Events

An adverse event that meets one or more of the following criteria/outcomes is classified as serious:

- Results in death
- Is life-threatening (i.e., at immediate risk of death)
- Requires in patient hospitalization or prolongation of existing hospitalization
- Results in persistent or significant disability/incapacity
- Results in congenital anomaly/birth defect
- Other important medical events that may not result in death, be life-threatening, or require hospitalization may be considered serious when, based upon appropriate medical judgment, they may jeopardize the patient or may require medical or surgical intervention to prevent one of the outcomes listed above. Examples of such events are intensive treatment in an emergency room for allergic bronchospasm; blood dyscrasias or convulsions that do not result in hospitalization; or the development of drug dependence or drug abuse.

5.3.5.2 Clinical Protocol

Serious also includes any other event that the Investigator or sponsor judges to be serious, or which is defined as serious by the HRA in the country in which the event occurred.

Progression of the malignancy under study (including signs and symptoms of progression) should not be reported as SAEs unless the outcome is fatal during the trial or within the safety reporting period. Hospitalizations due to signs and symptoms of disease progression should not be reported as SAEs. If the malignancy has a fatal outcome during the trial or within the safety reporting period, then the event leading to death must be recorded as an adverse event and as an SAE with CTC grade 5.

The onset date of an SAE is defined as the date on which the event initially met serious criteria (e.g., the date of admission to a hospital). The end date is the date on which the event no longer met serious criteria (e.g., the date the patient was discharged from a hospital).

8.2.2.1. Hospitalization

Adverse events associated with in-patient hospitalization, or prolongation of an existing hospitalization, are considered serious. Any initial admission, even if the duration is less than 24 hours is considered serious. In addition, any transfer within the hospital to an acute/intensive care unit is considered serious (e.g., transfer from the psychiatric wing to a medical floor or transfer from a medical floor to a coronary care unit). However, the following hospitalizations **should not** be considered serious:

- Rehabilitation facility admission
- Hospice facility admission
- Respite care
- Skilled nursing facility admission
- Nursing home admission
- Emergency room visit
- Outpatient same day surgery/procedure
- Hospitalization or prolongation of hospitalization in the absence of precipitating clinical adverse events as follows:
 - Admission for treatment of preexisting condition not associated with the development of a new adverse event or with a worsening of the preexisting condition
 - Social admission
 - Administrative admission (e.g. for yearly physical exam)
 - Protocol-specified admission during a clinical trial
 - Optional admission not associated with a precipitating clinical adverse event (e.g. for elective cosmetic surgery)
 - Preplanned treatments or surgical procedures that are not related to an SAE

5.3.5.2 Clinical Protocol

- Hospitalization for observation without an AE
- Diagnostic and therapeutic noninvasive and invasive procedures, such as surgery, should not be reported as adverse events. The medical condition for which the procedure was performed should be reported if it meets the definition of an adverse event (e.g. acute appendicitis that begins during the adverse event reporting period should be reported as an adverse event and the appendectomy should be recorded as a concomitant treatment).

8.3. Reporting Adverse Events

8.3.1. Eliciting Adverse Event Information

The Investigator is to report all directly observed adverse events and all adverse events spontaneously reported by the trial patient using concise medical terminology. In addition, each trial patient will be questioned about adverse events at each clinic visit following initiation of treatment. The question asked will be, “Since your last clinic visit have you had any health problems?”

8.3.2. Adverse Event Reporting Period

Safety information for each patient will be collected from the date of informed consent. Adverse events occurring prior to the initiation of the study treatment with pazopanib or TRC105 study drug will be considered "baseline-signs and symptoms", will be recorded on corresponding case report forms and will not be retained for patients who fail screening. The adverse event reporting period for this trial begins when the patient has received even a portion of the first dose of pazopanib or TRC105 study drug and ends 28 days after the last dose of pazopanib or TRC105 study drug is administered.

All adverse events that occur in trial patients during the adverse event reporting period specified in the protocol must be reported to TRACON, whether or not the event is considered study treatment-related. In addition, any known untoward event that occurs beyond the adverse event reporting period that the Investigator assesses as possibly related to the investigational medication/product should also be reported as an adverse event.

8.3.3. Reporting Requirements

Each adverse event is to be classified by the Investigator as SERIOUS or NONSERIOUS. This classification of the gravity of the event determines the reporting procedures to be followed. If an SAE occurs, reporting will follow local and international regulations, as appropriate.

The Investigator must notify the Sponsor of any event that meets one of the criteria for an SAE immediately upon learning of the event. Any subsequent revisions that are made to information pertaining to serious suspected TRC105 adverse drug reactions (e.g.,: change in grade etc.), including a change in attribution to TRC105 study drug from “not related” to “suspected adverse drug reaction” should also be communicated to TRACON immediately. This notification should be made to:

8.3.4. Recording Adverse Events in the Case Report Forms

The Investigator is to report all directly observed adverse events and all adverse events spontaneously reported by the trial patient. In addition, each trial patient will be questioned about adverse events. All adverse events that meet the criteria specified in Section 8.2.1 are to

5.3.5.2 Clinical Protocol

be recorded on patient source documents and on the CRFs. Adverse events should be reported using concise medical terminology on the CRFs.

8.3.5. Grading of Adverse Event Severity

To report adverse events on the CRFs, the Investigator will use the severity grading as described in NCI CTCAE (Version 4.0).

Every effort should be made by the Investigator to assess the adverse event according to CTCAE criteria. If the Investigator is unable to assess severity because the term is not described in NCI (Version 4.0), severity of MILD, MODERATE, SEVERE, LIFE-THREATENING, or FATAL may be used to describe the maximum intensity of the adverse event. For purposes of consistency, these intensity grades are defined as follows:

Table 16: Adverse Event Grading

Grade	Non-CTCAE Severity	Definition
1	Mild	Does not interfere with patient's usual function
2	Moderate	Interferes to some extent with patient's usual function
3	Severe	Interferes significantly with patient's usual function
4	Life-Threatening	Results in immediate risk of patient's death
5	Fatal	Results in patient's death

Note the distinction between the severity and the seriousness of an adverse event. A severe event is not necessarily a serious event. For example, a headache may be severe (interferes significantly with patient's usual function) but would not be classified as serious unless it met one of the criteria for serious events.

8.3.6. Relationship to TRC105 Study Drug/Pazopanib

In this study, TRC105 study drug is given in combination with Pazopanib. The relationship of an adverse event to TRC105 study drug and/or Pazopanib should be classified by the Investigator using the following guidelines:

- Suspected Adverse Reaction: There is a reasonable possibility that TRC105 caused the adverse event (i.e.: there is evidence to suggest a causal relationship between TRC105 and adverse event).
- Not Related: There is no reasonable possibility that the adverse event is associated with TRC105 study drug.

AE's related to TRC105 study drug or Pazopanib are considered Adverse Drug Reactions (ADR).

8.3.7. Expectedness

All TRC105 adverse events and adverse drug reactions are considered "unexpected" if it's not listed in the investigator brochure or not listed at the specificity or severity that has been observed. For example, under this definition, hepatic necrosis would be unexpected (by virtue of

5.3.5.2 Clinical Protocol

greater severity) if the investigator brochure referred only to elevated hepatic enzymes or hepatitis. Similarly, cerebral thromboembolism and cerebral vasculitis would be unexpected (by virtue of greater specificity) if the investigator brochure listed only cerebral vascular accidents. "Unexpected," as used in this definition, also refers to adverse events or suspected adverse reactions that are mentioned in the investigator brochure as occurring with a class of drugs or as anticipated from the pharmacological properties of the drug, but are not specifically mentioned as occurring with the particular drug under investigation.

All Pazopanib adverse events and adverse drug reactions are considered "unexpected" if it's not listed in the package insert or not listed at the specificity or severity that has been observed. "Unexpected," as used in this definition, also refers to adverse events or suspected adverse reactions that are mentioned in the package insert as occurring with a class of drugs or as anticipated from the pharmacological properties of the drug, but are not specifically mentioned as occurring with Pazopanib.

8.3.8. Exposure *in Utero*

If any trial patient (or partner of a trial patient) becomes or is found to be pregnant during the study or within 28 days of discontinuing the investigational medication/product, the Investigator must report the information to TRACON, or designee via the Pregnancy Notification Report Form. This must be done irrespective of whether an adverse event has occurred and within 24 hours of awareness of the pregnancy. The information submitted should include the anticipated date of delivery.

The Investigator will follow the patient (or partner of a trial patient) until completion of the pregnancy or until pregnancy termination (i.e., induced abortion) and then notify TRACON, or its designee, of the outcome within 5 days or as specified below. The Investigator will provide this information as a follow-up to the initial report. The reason(s) for an induced abortion must be specified.

The Investigator should follow procedures for reporting an SAE if pregnancy outcome meets criteria for an SAE (i.e., spontaneous abortion, stillbirth, neonatal death, or congenital anomaly [including that in an aborted fetus]).

In the case of a live birth, the "normality" of the newborn can be assessed at the time of birth and the Pregnancy Outcome Report Form should be completed (i.e., no minimum follow-up period of a presumably normal infant must pass before a Pregnancy Outcome Report Form can be completed). The "normality" of an aborted fetus can be assessed by gross visual inspection unless pre-abortion laboratory findings are suggestive of a congenital anomaly.

Additional information about pregnancy outcomes that are classified as SAEs follows:

- "Spontaneous abortion" includes miscarriage and missed abortion.
- All neonatal deaths that occur within 1 month of birth should be reported, without regard to causality, as SAEs. In addition, any infant death after 1 month that the Investigator assesses as possibly related to the *in utero* exposure to the investigational medication should also be reported.

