5.3.5.2 Clinical Protocol

months following last dose of TRC105. All female patients of reproductive potential must have a negative pregnancy test (serum or urine) within 7 days prior to first dose. Male patients must be surgically sterile or must agree to use effective contraception during the study and for 3 months following last dose of TRC105. The definition of effective contraception will be based on the judgment of the Principal Investigator or a designated associate.

20. Other severe acute or chronic medical or psychiatric condition or laboratory abnormality that may increase the risk associated with study participation or may interfere with the interpretation of study results and, in the judgment of the Investigator, would make the patient inappropriate for this study

TRC105 investigational product dose and mode of administration:**Phase 1b**

Dosing will begin at 8 mg/kg (Dose Level 1); however a -1 Dose Level has also been included (6 mg/kg) and will be enrolled if 8 mg/kg is found to exceed the MTD.

For Dose Level -1, 1, 2 and Expanded Cohort 1, following the appropriate premedication regimen, the first weekly TRC105 dose (cycle 2 day 1) will be split into two doses whereby 3 mg/kg is administered on cycle 2 day 1 and the balance (e.g., 5 mg/kg for Dose Level 1) is administered on cycle 2 day 4. Beginning with cycle 2 day 8 and thereafter, the full (e.g., 8 mg/kg for Dose Level 1) TRC105 dose will be administered i.v. weekly during each 28-day cycle.

For Dose Levels 3, and Expanded Cohort 2, following the appropriate pre-medication regimen, TRC105 will be administered weekly at a dose of 10 mg/kg during cycle 1. The first weekly TRC105 dose will be split into two doses whereby 3 mg/kg is administered on cycle 1 day 1 and the balance is administered on cycle 1 day 4. Beginning with cycle 1 day 8 and for the rest of cycle 1, the full (e.g., 10 mg/kg) TRC105 dose will be administered i.v. weekly. Starting on cycle 2 day 1 and beyond, TRC105 will be administered at a dose of 15 mg/kg (Dose Level 3) every two weeks on days 1 and 15 of each 28-day cycle.

Phase 2

Patients will receive pazopanib once daily and following appropriate premedication regimen will receive TRC105 at 3 mg/kg on cycle 1 day 1, 7 mg/kg on cycle 1 day 4, and 10 mg/kg on cycle 1 day 8 and weekly thereafter. Each cycle is 28 days in duration. TRC105 dose modification is allowed beginning with cycle 2.

Angiosarcoma cohort 1

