5.3.5.2 Clinical Protocol

Bone Scans:

A bone scan is a test that can find cancer that has spread to the bones. A bone scan can often find a problem days to months earlier than a regular X-ray test. During a bone scan, a radioactive substance called a tracer is injected into a vein in your arm. The tracer travels through your bloodstream and into your bones. Then a special camera takes pictures of the tracer in your bones. A bone scan poses no greater risk than do conventional X-ray procedures. The tracers used in a bone scan produce very little radiation exposure — less than half that of a CT scan.

Venipuncture

Patients could also experience side effects from venipuncture for tests that will be done as part of this study including pain, tenderness or bruising at the site of collection, and rarely infection may occur at the spot where the needle is inserted.

Other Risks

This study treatment may involve risks to unborn children therefore patients should not become pregnant or father a baby while participating in this study. Patients should not nurse while on this study. Women of childbearing potential must have a negative pregnancy test before taking part in this study. Patients will be asked to practice an effective method of birth control during participation in this study and for three months after the last treatment. The long term risk of infertility is unknown. Ovarian failure has been observed with other antiangiogenic agents.

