8. **Hematology, Chemistry & Coagulation:** Testing to be performed locally. Thyroid stimulating hormone to be tested at screening, day 1 of each cycle and at the end of study visit. Cycle 1 day 1 assessments only need to be performed if screening assessments were performed more than 7 days prior to cycle 1 day 1. Iron studies (FE) to be performed according to the schedule of assessments and as clinically indicated during the study. Lab assessments may be performed within 3 days prior to TRC105 dosing. In addition to the assessments scheduled for the clinical trial, patients should undergo assessment as appropriate to ensure safe treatment. See Section 8.1.1.1 for specific panel collection requirements.
9. **Pregnancy Test:** Testing to be performed locally. All female patients of childbearing potential must have a negative serum or urine pregnancy test within 7 days of cycle 1 day 1 and 28 days following the last dose of TRC105.
10. **Urinalysis:** To be performed locally. Cycle 1 day 1 urinalysis only needs to be performed if screening urinalysis was performed more than 7 days prior to cycle 1 day 1. Microscopic analysis and/or urine protein creatinine ratio or 24-hour urine protein collection should be performed as clinically indicated.
11. **TRC105 Administration:** Intravenous TRC105 diluted in normal saline will be administered every 7 days. The first weekly TRC105 dose will be given on cycle 1 day 1 and split into two doses whereby 3 mg/kg is administered on cycle 1 day 1 and the balance is administered on cycle 1 day 4. The entire weekly dose of TRC105 (10 mg/kg) is then given on cycle 1 day 8 and weekly thereafter. See Section 6.1.6 for specific TRC105 administration guidelines.
 - **Upon completion of enrollment of phase 1b dose levels 3 and notification by the sponsor, active patients that are past cycle 2, may be switched to an every 2 week dosing schedule at the every 2 week dosing MTD.**
12. **Pazopanib Dosing:** Oral pazopanib will be dosed once daily at 800 mg starting on cycle 1 day 1 in the absence of toxicity on days 1-28 of each 28 day cycle according to the pazopanib package insert. Dose reductions are allowed based on individual patient tolerability beginning with cycle 1. See Section 6.2 for specific dosing guidelines. Pazopanib should be dosed following PK collection on cycle 1 day 1 and day 1 of even cycles.

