18. **TRC105 and Pazopanib Pharmacokinetics Trough Concentration:** A 5 mL blood sample each for TRC105 and pazopanib pharmacokinetics to be collected at the time-points indicated in the Schedule of Assessments, prior to starting the TRC105 infusion and prior to pazopanib dosing. Samples will be stored at approximately -70°C. Samples will be batch shipped as indicated in the laboratory manual to a third-party laboratory. See separate laboratory guide for further collection and shipment information. Additional PK samples may also be collected at the time of unexpected clinical events.
19. **Protein Biomarkers:** One 10 mL purple top (K₃EDTA) tube will be collected at the time-points indicated in the schedule of assessments and stored at approximately -70°C to be analysed by a central laboratory. See separate laboratory guide for further collection and shipment information.
20. **Archival Tumor Tissue:** Archival specimens (formalin-fixed, paraffin-embedded) are required of the primary cancer and/or metastatic cancer specimen for each study participant. It is preferable that the entire paraffin block be submitted, but if this is not feasible, then at least 20 unstained slides are requested for immunohistochemical analysis (sections of 5 microns are preferred). See separate laboratory guide for further collection and shipment information.
21. **Cycle 2+ Treatment:** Patients who demonstrate a response of CR, PR or SD will be eligible for additional treatment until progression.
22. **Follow-up:** The follow-up visit should occur 28 days following the last dose of TRC105. The allowable visit window is +/- 7 days.
23. Allowable window for each visit within the cycle is +/- 2 days unless otherwise stated.

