5.3.5.2 Clinical Protocol

11. Active bleeding or pathologic condition that carries a high risk of bleeding (e.g. hereditary hemorrhagic telangiectasia). Patients who have been uneventfully anti-coagulated with low molecular weight heparin are eligible.
12. Thrombolytic use (except to maintain i.v. catheters) within 10 days prior to first day of study therapy
13. Known active viral or nonviral hepatitis or cirrhosis
14. History of hemorrhage or hemoptysis (> ½ teaspoon bright red blood) within 3 months of starting study treatment
15. History of peptic ulcer within 3 months of treatment, unless treated for the condition and complete resolution has been documented by esophagogastroduodenoscopy (EGD) within 28 days of starting study treatment
16. History of gastrointestinal perforation or fistula in the past 6 months, or while previously on antiangiogenic therapy, unless underlying risk has been resolved (e.g., through surgical resection or repair)
17. Known human immunodeficiency virus (HIV) or acquired immunodeficiency syndrome (AIDS) related illness
18. Receipt of a strong CYP3A4 inducer within 12 days prior to cycle 1 day 1 or a strong CYP3A4 inhibitor within 7 days prior to cycle 1 day 1 ([Table 14](#))
19. Pregnancy or breastfeeding. Female patients must be surgically sterile (i.e.: hysterectomy) or be postmenopausal, or must agree to use effective contraception during the study and for 3 months following last dose of TRC105. All female patients of reproductive potential must have a negative pregnancy test (serum or urine) within 7 days prior to first dose. Male patients must be surgically sterile or must agree to use effective contraception during the study and for 3 months following last dose of TRC105. The definition of effective contraception will be based on the judgment of the Principal Investigator or a designated associate.
20. Other severe acute or chronic medical or psychiatric condition or laboratory abnormality that may increase the risk associated with study participation or may interfere with the interpretation of study results and, in the judgment of the Investigator, would make the patient inappropriate for this study

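### Mandatory pregnancy reporting stops 28 days after study product, while contraception is required for 3 months, so pregnancies conceived from day 29 to month 3 need not be notified or followed

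*Combined protocol and SAP*

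**What the plan says.** **Reporting.** Under Section 8.3.8 (Exposure in Utero), the investigator must notify the sponsor if a patient or partner "becomes or is found to be pregnant during the study or within 28 days of discontinuing the investigational medication/product". The duty applies whether or not an adverse event has occurred. The investigator must then follow the pregnancy to its end and report the outcome, including a normal one.

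**Contraception.** Section 8.1.1.1 and exclusion criterion 19 (Synopsis and Section 5.2) say that female patients who are not sterile or postmenopausal "must agree to use effective contraception during the study and for 3 months following last dose of TRC105". Criterion 19 sets the same period for men: "Male patients must be surgically sterile or must agree to use effective contraception during the study and for 3 months following last dose of TRC105". Section 2.5.1 (Other Risks) says that treatment may carry risks for unborn children, and then gives this instruction: "practice an effective method of birth control during participation in this study and for three months after the last treatment".

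**Testing and visits.** The phase 2 soft tissue sarcoma schedule (Table 6, footnote 9) asks women who could conceive for a negative test in the week before treatment starts and another 28 days after TRC105 ends. Footnote 22 fixes the last visit: "The follow-up visit should occur 28 days following the last dose of TRC105. The allowable visit window is +/- 7 days". The other three schedules also place the last pregnancy test 28 days after the last TRC105 dose.

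**The concern.** The protocol asks both sexes to avoid conception for 3 months after treatment, but its pregnancy-specific reporting rule ends after 28 days. Nothing in the text explains why reporting stops first. A pregnancy conceived in between falls within the period the protocol itself treats as calling for precaution, yet it triggers neither the notification form nor follow-up to outcome.

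What is at stake is safety information, not an endpoint or an error rate. Section 2.1.2 describes the drug target as essential to vascular development: mice lacking CD105 die before birth. Patients may enrol from age 12, and those with reproductive potential are eligible. Few exposed pregnancies are likely, so each is informative for an investigational antibody. Section 8.3.8 is deliberately broader than the adverse event rules because it also collects uncomplicated pregnancies and normal outcomes. That breadth is what is lost after day 28.

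**Working it through.** The documents state no figure on this point, so there is nothing to reproduce. The check has two parts.

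**1. Length of the gap**

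Inputs: post-treatment reporting window of 28 days (Section 8.3.8); contraception period D of 3 months (criterion 19, Sections 2.5.1 and 8.1.1.1). The protocol does not convert 3 months to days, so D is varied as an assumption. For this part both clocks are taken to start on the same day.

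Uncovered days = D − 28. Uncovered share = 1 − 28/D.

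| Meaning of 3 months | D (days) | Uncovered days | Uncovered share |
|---|---|---|---|
| Three 28-day cycles | 84 | 56 | 66.7% |
| Shortest calendar span | 89 | 61 | 68.5% |
| Quarter of a year (365.25/4) | 91.3 | 63.3 | 69.3% |
| Longest calendar span | 92 | 64 | 69.6% |

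Sensitivity: suppose the follow-up test falls at the late edge of its window, day 28 + 7 = 35, and a pregnancy found then is counted as covered. The share is then 1 − 35/91.3 = 61.7%.

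**2. What covers a pregnancy, by when it begins**

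- *During the study:* covered by Section 8.3.8. Withdrawal criterion 6 in Section 5.3 separately requires follow-up of patients who become pregnant on treatment.
- *By day 28 after discontinuation, detected at any time:* covered. Section 8.3.8 applies to a pregnancy that arises in the window as well as to one discovered in it.
- *From day 29 to month 3:* no pregnancy notification is required. Section 8.3.2 ends the adverse event period 28 days after the last dose of either drug. After that, Sections 8.3.2 and 4.1.4 and footnote 16 of the schedules require reports only of events judged related or possibly related. An uncomplicated pregnancy in a patient or partner meets none of these conditions.

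**3. Starting points**

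Criterion 19 and Section 8.1.1.1 count from the last TRC105 dose, Section 2.5.1 from the last treatment, and Section 8.3.8 from discontinuing the investigational product. Section 5.3 lets some patients continue on pazopanib alone. If such a patient takes pazopanib for x days after the last TRC105 dose, and reporting runs to 28 days after pazopanib stops, the gap against criterion 19 is D − 28 − x. With D = 91.3 and an assumed x of 56 (two cycles), it is 91.3 − 28 − 56 = 7.3 days. Counted from last treatment, as in Section 2.5.1, it stays at 63.3 days. The 56 to 64 days is therefore a maximum.

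**The case against.** **Most exposure time is covered.** A reader might infer that two thirds of the whole contraception period lies outside the reporting rule. It does not: that period also includes time on study, which Section 8.3.8 covers. Taking 3 months as 91 days (gap 63 days), and assuming times on treatment of 56, 140 or 210 days, the uncovered shares of the full period are 63/147 = 43%, 63/231 = 27% and 63/301 = 21%. The 67% to 70% applies only to the post-treatment part. This objection stands.

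**Harm would still be reported.** A reader might infer that a damaged pregnancy could go unreported without breach of the protocol simply because it began after day 28. The documents do not support that as a general statement. Section 8.2.1 lists signs resulting from exposure in utero as adverse events, Section 8.2.2 makes congenital anomaly a seriousness criterion, and known events judged possibly related stay reportable after the period. This stands too, but only in part. It does not reach uncomplicated pregnancies or outcomes judged unrelated, and it requires the investigator to learn of the outcome without any duty to follow the pregnancy.

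**The windows need not match.** Contraception is a precaution, and the documents do not say that fetal exposure lasts 3 months. The 28 days agree with the adverse event period, the last test and the last visit. That is a fair account of how the rule may have arisen. It does not explain why the one provision designed for exposed pregnancies should end before the precaution against them.

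**"During the study" could mean the whole trial.** Section 15.1 ends the trial when all patients have completed treatment, so early patients would be covered for longer. But coverage would then depend on calendar date rather than exposure, and the 28-day limit would have little function. This reading does not resolve the mismatch.

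**Conclusion.** The mismatch is real and limited. Pregnancies of patients or partners conceived from day 29 to month 3 after treatment have no mandatory notification and no required follow-up to outcome. The gap is at most about 56 to 64 days, or 67% to 70% of the post-treatment contraception period. This assumes that both clocks start together and that 3 months is between 84 and 92 days. It is shorter, or absent, when contraception is counted from the last TRC105 dose and pazopanib continues.

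The size is in days of coverage, not expected pregnancies, for which the documents give no basis. The documents do not support saying that pregnancies during the study, or those begun by day 28 and found later, escape the rule, or that possibly related harm goes unreported. No sample size, endpoint or error rate is affected. This is a minor safety-reporting inconsistency that is cheap to correct.

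**What to change.** Reconcile Section 8.3.8 with criterion 19 and Sections 2.5.1 and 8.1.1.1. Extend the post-treatment reporting window in Section 8.3.8 to the contraception period the protocol already states, and leave that period unchanged. Count both from a single starting point, named identically in all these places and explicit about patients who continue one drug alone. For the last patients to stop, say that the duty continues past the end of trial as Section 15.1 defines it; the 28-day rule already does so.

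The cost is a short text change and a few extra reports followed to outcome. It adds at most 56 to 64 days to the reporting window and requires no new visit, test or change to treatment. Its limit is detection: with nothing scheduled after the 28-day visit (± 7 days), the investigator would have to learn of a later pregnancy from the patient or partner. Asking patients at that visit to report one would help, but would not guarantee capture.
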